2.0 Objectives*

- 2.1 The purpose of this investigation is to examine the effects of carbohydrate vs. carbohydrate-protein co-ingestion vs. placebo on a subsequent bout of performance following high-intensity exercise and a 2-hour recovery period in Masters Class Athletes.
- 2.2 It is hypothesized that:
 - Carbohydrate will improve subsequent performance significantly better than the placebo post-exercise in male Masters Class Athletes.
 - Carbohydrate and protein will improve subsequent performance significantly better than PLA post-exercise in male Masters Class Athletes.
 - Carbohydrate and Protein will not improve subsequent performance significantly better than CHO post-exercise in male Masters Class Athletes.

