17.0 Data Management* and Confidentiality

17.1 All statistical analyses will be conducted via the Statistical Package for Social Science (SPSS) software for Windows version 21 (SPSS Inc., Chicago, IL). Data will be statistically analyzed using separate 1-way analysis of covariance (ANCOVA) for TTE, HRV-Slope Recovery, and Sweat Rate measures. The pretest and

the posttest values will be used as a covariate and dependent variable, respectively. If the ANCOVA is significant, Fisher's LSD Post-Hoc analysis will be used to determine group differences. For effect size (ES), the partial eta squared statistic will be reported, with 0.01, 0.06, and 0.14 representing small, medium, and large ES, respectively. The significance level will be set at $p \leq 0.05$.

17.2 The calculation of sample size (G*Power 3.1.9.4) was based on pilot data in low-to-moderately trained young men (22.1 + 3.2 years) collected in our lab using the same protocol (90% PPO TTE) as outlined in this study. The total sample size was determined to be a total of 18 (6 in each group) based on a one-way ANCOVA, power of 0.90, and an alpha of 0.05. However, due to potential dropout rates, a total of 30 participants (10 per group) will be recruited with the goal of completing 18.

17.3 Individual results will remain confidential and only be related to the participant upon request once the study is completed. All questionnaires and data collection sheets will be kept in a locked cabinet during and following the study. Data that is electronically stored will be kept on a password-protected computer in the office of the investigator who oversees data collection. All information will be destroyed six years from the end of the study. Participant folders will be marked with an I.D. number to protect against a breach of confidentiality. Participant names and I.D. numbers will be stored apart from the subject folders in a password protected electronic file.

17.4 Quality control of collected data will be performed by ensuring all data files remain in filing cabinets when not in use.

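### When the omnibus ANCOVA is non-significant, section 17.1 plans no pairwise difference or interval, although the hypotheses in 2.2 are three pairwise comparisons

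*Combined protocol and SAP*

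**What the plan says.** Section 2.2 makes three directional statements about named pairs. The first sets CHO against PLA: "Carbohydrate will improve subsequent performance significantly better than the placebo post-exercise in male Masters Class Athletes". The second makes the same superiority claim for CHO-P over PLA. The third compares the two active drinks and expects no added benefit from protein: "Carbohydrate and Protein will not improve subsequent performance significantly better than CHO post-exercise in male Masters Class Athletes".

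Section 17.1 analyses the outcomes by "separate 1-way analysis of covariance (ANCOVA) for TTE, HRV-Slope Recovery, and Sweat Rate measures", with the pretest value as covariate. Pairs come second and depend on a significant F test; only in that event is it planned that "LSD Post-Hoc analysis will be used to determine group differences". The one effect measure named is an overall statistic, not a pairwise one: "For effect size (ES), the partial eta squared statistic will be reported". The documents contain no planned contrast, pairwise adjusted mean difference or confidence interval.

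Section 17.2 sizes the trial at 18 completers, 6 per group, for a one-way ANCOVA with power 0.90 and alpha 0.05, and recruits 30 (10 per group) to allow for dropout. The effect size behind the 18 is not given. The primary objective in the Study Summary (section 1.0) runs differently from 2.2: it sets out to show that performance does not differ significantly whichever drink is taken, placebo included.

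**The concern.** The omnibus F test has 2 numerator degrees of freedom and asks whether the three adjusted means are all equal. None of the hypotheses in 2.2 asks that. Partial eta squared does not fill the gap, because it does not say which drink differs, in which direction, or by how many seconds of time to exhaustion.

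If F is significant, LSD at least identifies pairs. If it is not, the plan followed as written ends with a p-value and an overall effect size, and the three comparisons have no planned answer. A non-significant F is then easily reported as no difference between drinks. Two features make that reading more likely: the objective in section 1.0 is worded as absence of a significant difference, and the third hypothesis in 2.2 is a no-benefit statement with no margin. In a trial this small, such a conclusion could sit alongside differences that are large in either direction.

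**Working it through.** **Inputs.** Three equal groups and one covariate, so the error df are N − 4 (17.1). n = 6 or 10 per group, N = 18 or 30 (17.2). Alpha is 0.05; sidedness is not stated, so two-sided is assumed. The unit is the covariate-adjusted (residual) SD, because no SD is given. Sections 1.0 and 12.2 also give 50 as an enrolment ceiling; I use the completer target and recruitment number from 17.2.

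**Step 1. The plan's own figure.** N = 18 cannot be reproduced without an effect size, only back-solved. With noncentrality λ = f²N and df (2, 14), power 0.90 needs f = 0.938:

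- λ = 0.938² × 18 = 15.8
- partial eta squared = f²/(1 + f²) = 0.880/1.880 = 0.47

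For the pattern in 2.2 (PLA = 0, both active drinks = d), f = d√2/3, so d = 0.938 × 3/√2 = 1.99 SD.

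**Step 2. What a pairwise interval would show.** Half-width = t(0.975, N − 4) × √(2/n), taking the covariate as balanced across groups:

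- n = 6: 2.145 × 0.577 = 1.24 SD
- n = 10: 2.056 × 0.447 = 0.92 SD

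An observed difference of zero would therefore be compatible with a true difference of up to about 1.24 SD (or 0.92 SD) in either direction.

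**Step 3. Error control.** Simulation under the global null, N = 18:

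- any false pairwise claim, omnibus then LSD: 5.0%
- any of three ungated LSD tests at 0.05: 11.6%

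The gate does the multiplicity work. The 11.6% is also the chance that at least one of three unadjusted 95% intervals excludes zero.

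**Step 4. What the gate costs in power.** The comparator is a 1-df contrast gate (PLA against the mean of CHO and CHO-P), then each active drink against PLA at 0.05. Both active drinks are d better than PLA. The values 1.0 and 1.5 are assumptions; 1.99 is from step 1. Each cell gives omnibus gate, then contrast gate.

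| d (SD) | N | Gate passes | Each active vs PLA | Both active vs PLA |
|---|---|---|---|---|
| 1.0 | 18 | 0.34, 0.46 | 0.275, 0.33 | 0.21, 0.22 |
| 1.5 | 18 | 0.67, 0.80 | 0.60, 0.66 | 0.52, 0.54 |
| 1.99 | 18 | 0.90, 0.96 | 0.86, 0.89 | 0.82, 0.83 |
| 1.0 | 30 | 0.58, 0.70 | 0.49, 0.55 | 0.41, 0.42 |

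For the comparisons that 2.2 names, the omnibus gate costs about 5 points per pair at 1.0 SD, 6 at 1.5 SD and 3 at 1.99 SD. For confirming both superiority claims it costs about 1 point.

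**Step 5. The reverse pattern.** If only CHO-P works (1.0 SD, N = 30), the chance of passing the gate is 0.58 for the omnibus test and 0.24 for the contrast. Power for CHO-P against PLA is 0.49 and 0.23 respectively.

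**The case against.** The strongest defence is that omnibus-then-LSD is a recognised and valid procedure for three groups, and that 17.1 gates tests, not estimates. Nothing in it forbids printing adjusted means or differences. Both points stand. The accurate statement is that no pairwise estimate is planned, not that one is excluded. A prespecified plan should nevertheless not leave the answers to its own hypotheses to discretion after the F test is seen.

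A reader might go further and infer that the gate forfeits so much power that a planned contrast must replace it. The documents do not support that. The 12-point gap between 0.34 and 0.46 concerns a pooled contrast that is not one of the hypotheses in 2.2 either; for the named pairs the loss is the smaller one in step 4. The contrast does badly if only one active drink works, and the background (3.0) makes that pattern conceivable: it cites better later performance, or a smaller decline, with CHO-P co-ingestion in younger athletes. The contrast gate, with its two active-against-PLA tests, also leaves CHO-P against CHO untested. And it presupposes that 2.2 governs, whereas the objective in 1.0 and the non-directional purpose in 2.1 suit an omnibus test.

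Nor do the figures show that a non-significant omnibus result is generally likely. That holds at 1.0 SD with N = 18 (power 0.34), but not at 1.0 SD with N = 30 (0.58) or at 1.5 SD with N = 18 (0.67).

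Finally, three intervals shown regardless of the gate carry a multiplicity risk of 11.6% under the global null at N = 18. That is a fair objection to unlabelled intervals, and the fix has to meet it.

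**Conclusion.** The point holds as a gap in planned estimation. Section 2.2 asks about three pairs; 17.1 commits to a pairwise result only if F is significant, and to no pairwise estimate in any case. A non-significant result could then be read as no difference while the unreported intervals extend about 1.24 adjusted SD (6 per group) or 0.92 SD (10 per group) either side of the estimate. These half-widths assume equal groups, a balanced covariate and N − 4 error df; they need no effect size.

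The power figures do need one, and the plan gives none, so each is conditional on an assumed d or on the 1.99 SD back-solved from N = 18 and 90% power. They show a modest cost of the gate for the hypothesised pairs and a larger cost of the alternative when one drink works alone. Error control is not at fault. Replacing the gate is an optional trade-off, not a correction.

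**What to change.** In 17.1:

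1. Report the covariate-adjusted mean differences CHO − PLA, CHO-P − PLA and CHO-P − CHO with 95% confidence intervals for TTE, in seconds, whatever the omnibus result. Do the same for HRV slope and sweat rate in their own units.
2. Keep the omnibus gate for significance claims. Label the intervals as estimates, unadjusted for multiplicity and not a basis for claims when the omnibus test fails.
3. State that a non-significant omnibus or pairwise result is not evidence of equivalence. Supporting the third hypothesis in 2.2 positively would need a prespecified margin set against the CHO-P − CHO interval.

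The objective in 1.0 and the hypotheses in 2.2 should be reconciled. A PLA-against-actives contrast could be considered only after that, with the one-drink scenario weighed openly.

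The cost is a few sentences in the plan and three extra rows per outcome: no further participants, measurements or alpha. The one downside is the 11.6% chance under the global null at N = 18 that some interval excludes zero, which the label in item 2 addresses.

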6.0 Procedures Involved*

6.1 To test the hypothesis, this study will utilize a randomized, double-blind, placebo-controlled between-subject design to examine the effects of CHO and CHO-P supplementation on short-term recovery following aerobic interval exercise and time to exhaustion testing in MCA's. After completing the informed consent and screening process (Visit #1), each participant will be assessed for their anthropometric measures as well as body composition and will complete a GXT to volitional exhaustion on a cycle ergometer to determine VO₂peak. Participants will also be provided with the option to return to the lab on a separate date for the GXT and VO₂peak testing. Forty-eight to 72 hours after Visit #1, or VO₂peak testing, participants will return to the lab for familiarization with the INT exercise protocol and TTE (Visit #2). Within five to nine days after familiarization (Visit #2), participants will return to the lab for Visit #3 to complete INT exercise and TTE, a 2-hour passive recovery period including the consumption of one of three treatments (CHO, CHO-P, PLA), followed by repeated INT exercise and TTE, HRV and SR determination. Participants will also complete the Nutritional Recovery Practices, Knowledge, and Beliefs of Australian Triathletes survey during the 2-hour recovery period. Participants will be asked to complete the ASA24®, an automated self-administered 24-hour dietary assessment tool during the 5-9-day period between familiarization (Visit #2) and the experimental protocol (Visit #3).

Testing Procedures.

- Participants will report to the testing location on 3 separate occasions.
- Visit #1: The study will be explained to the participant by the investigators. Participants will be asked to provide their written, informed consent. The participants will then be asked to complete the American College of Sports Medicine Exercise Preparticipation Health Screening Questionnaire for Exercise Professionals (PHSQEP), Physical Activity Readiness Questionnaire for Everyone (PAR-Q+), and Medical Health and Activity Questionnaire.

Following the written consent and screening process, anthropometrics and body composition will be measured, and the VO₂peak test outlined in section 6.3 will be completed. Following informed consent, screening, and anthropometrics and body composition, if necessary (i.e., due to time constraints), participants may choose to return to the lab on a separate occasion for VO₂peak testing.

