12.0 Local Number of Subjects

12.1 All participants will be recruited from the University of Central Florida and from within the surrounding Central Florida area.

12.2 Participants will be recruited and screened until a maximum of 50 individuals are enrolled. Participants will be considered enrolled only after an informed consent document has been signed, a medical history questionnaire, PHSQEP and PAR-Q+ have been completed, and anthropometric data have been recorded. To account for individuals who do not meet the inclusion criteria, the number of recruited individuals will likely exceed the number of enrolled participants. However, no more than 50 participants will be recruited.

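### At the planned 18 completers, partial eta squared read against fixed 0.01/0.06/0.14 labels would call ineffective drinks a medium or large effect in about 65% of analyses

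*Combined protocol and SAP*

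**What the plan says.** Section 17.1 plans "separate 1-way analysis of covariance (ANCOVA) for TTE, HRV-Slope Recovery, and Sweat Rate measures". The model is an adjustment for the first-bout value: the pretest and "the posttest values will be used as a covariate and dependent variable, respectively". The F test is judged at the 0.05 level, and Fisher's LSD comparisons follow only if it is significant.

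The effect-size sentence carries no such condition: "the partial eta squared statistic will be reported, with 0.01, 0.06, and 0.14 representing small, medium, and large ES, respectively". Section 17.1 mentions no bias-corrected index, no confidence interval and no difference in the outcome's own unit.

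Section 17.2 gives the planned size: "The total sample size was determined to be a total of 18 (6 in each group) based on a one-way ANCOVA". It adds that "a total of 30 participants (10 per group) will be recruited with the goal of completing 18". Section 12.2 gives a different ceiling: "Participants will be recruited and screened until a maximum of 50 individuals are enrolled".

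**The concern.** Partial eta squared is the share of covariate-adjusted variation that the sample attributes to the drinks. Group means differ by chance even when the drinks are equivalent, so the share is always positive. The fewer the error degrees of freedom, the larger it is on average. Fixed cut-offs take no account of this. At 18 completers the chance component alone is about twice the medium cut-off and close to the large one.

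This matters for the question the trial asks. Section 1.0 sets out to show that performance does not differ significantly between drinks, while section 2.2 expects both active drinks to beat placebo and the protein drink not to beat carbohydrate alone. A reader must therefore separate a negligible difference from a real one. A label that often reads medium or large when nothing is happening does not help, and it can attach a sizeable-sounding effect to a result with p > 0.05.

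**Working it through.** **Inputs**
- Three groups: section 6.1, "consumption of one of three treatments (CHO, CHO-P, PLA". Numerator df = 2.
- One covariate, the pretest value: section 17.1.
- N = 18, six per group: section 17.2. Error df = 18 − 3 − 1 = 14.
- Cut-offs 0.01, 0.06 and 0.14, and alpha 0.05: section 17.1.
- N = 30 (section 17.2) and N = 50 (section 12.2) as sensitivity values.

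**The plan's own figure.** The sample size of 18 cannot be reproduced, because the effect size taken from the pilot data is not given. For 90% power with this model, N = 18 implies a Cohen's f of at least about 0.94, a population partial eta squared of about 0.47. Nothing below depends on that value.

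**Distribution with no drink effect.** Partial eta squared = 2F/(2F + error df). With normal errors of equal variance it follows Beta(1, (N − 4)/2), so:
- mean = 2/(N − 2)
- P(at least c) = (1 − c)^((N − 4)/2)

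At N = 18 this is Beta(1, 7):
- mean = 2/16 = 0.125
- at least small: 0.99^7 = 93.2%
- medium or large: 0.94^7 = 64.8%
- large: 0.86^7 = 34.8%

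**Value needed for significance.** Critical F(2, 14) = 3.739, so partial eta squared must reach 7.478/(7.478 + 14) = 0.348. That this matches the 34.8% above is coincidence. All of the significant 5% lie above 0.14, so with no drink effect 34.8 − 5 = 29.8% of analyses are labelled large with p > 0.05, and 64.8 − 5 = 59.8% are labelled medium or large with p > 0.05.

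**Other sample sizes, no drink effect**

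| Analysed | Mean | Medium or large | Large | Needed for p ≤ 0.05 |
|---|---|---|---|---|
| 18 | 0.125 | 64.8% | 34.8% | 0.348 |
| 30 | 2/28 = 0.071 | 0.94^13 = 44.7% | 0.86^13 = 14.1% | 0.206 |
| 50 | 2/48 = 0.042 | 0.94^23 = 24.1% | 0.86^23 = 3.1% | 0.122 |

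At 50 the critical value falls below 0.14, so a large label there always comes with p ≤ 0.05. A medium label without significance remains possible.

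**Simulation check.** 100,000 ANCOVAs with six per group, at each of three pre-post correlations (0, 0.5, 0.9), gave means of 0.125, medium or large in 64.8 to 64.9%, and large in 34.7 to 35.0%. The correlation made no difference to the null result.

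**Without a usable covariate.** Section 6.1 schedules the 30-minute HRV recording after the second bout, so it is unclear whether a pretest HRV slope exists. With no covariate, error df = 15: mean 2/17 = 0.118, medium or large 0.94^7.5 = 62.9%. The conclusion is the same.

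**Corrected index at N = 18.** Partial epsilon squared = 1 − (1 − partial eta squared) × 16/14. Its null mean is 1 − 0.875 × 16/14 = 0. It reaches 0.06 in (0.94 × 14/16)^7 = 0.8225^7 = 25.5% of null analyses and 0.14 in (0.86 × 14/16)^7 = 0.7525^7 = 13.7%. It is negative in 1 − 0.875^7 = 61%.

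**Secondary point: covariate strength.** A partial index leaves out the variation that the pretest explains, so one difference in seconds earns a bigger value when the two bouts correlate more. Take 0.06 without the covariate: f² = 0.06/0.94 = 0.0638. Dividing by (1 − r²) and converting back gives 0.091, 0.111 and 0.151 at r = 0.6, 0.7 and 0.8. These correlations are assumed; the documents give none.

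**The case against.** The strongest reply is that nothing is decided by the labels. Inference runs through the F test and, if that is significant, LSD; no hypothesis or conclusion rule refers to a medium or large effect; and a large label with p > 0.05 would be printed next to its p-value. That stands, and it limits the point to reporting. A reader might infer that the bias inflates false positive findings. It does not: the F test is untouched.

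Second, 18 is the smallest of the sample sizes the protocol mentions, and the bias shrinks at 30 or 50. That also stands, and is why the range is shown. But 18 is the number the plan aims to complete, and at 30 almost half of null analyses are still labelled medium or large.

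Third, the corrected index is a monotone function of the same F and still varies widely at 18. This is true. It removes the average bias, not the noise. A reader might infer that partial eta squared is what would hide a real but modest effect; that difficulty comes from the small sample, and no choice of index cures it.

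Fourth, leaving out covariate variation is what a partial index is defined to do, so it is not an error, and epsilon squared shares the property. Only differences in original units deal with it.

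A reader might also multiply across the three outcomes to get the chance that at least one is labelled large. The documents do not support the independence this needs: in section 6.1 sweat rate is calculated from total exercise time, which includes the time to exhaustion.

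**Conclusion.** The point holds as a reporting flaw that should be corrected. Followed as written, section 17.1 gives an upward-biased effect size with a label that is often wrong when the drinks do not differ: mean 0.125, about 65% medium or large and about 35% large at 18 completers, falling to 0.042, 24% and 3% if 50 were analysed. At 18 or 30, every significant result is large by construction, so the label adds nothing to the p-value there.

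The figures assume no true drink effect, normal errors of equal variance, three groups and one covariate. They do not depend on the unreported pilot effect size or on the pre-post correlation. They do not show that the test is invalid.

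**What to change.** In section 17.1:
- Delete the 0.01/0.06/0.14 labels.
- If a variance-explained index is kept, report a bias-corrected one. For three groups and one covariate, partial epsilon squared = 1 − (1 − partial eta squared) × (N − 2)/(N − 4), with N the number analysed; omega squared is an alternative. Report negative values as they are.
- For each outcome, give the covariate-adjusted differences between drinks with 95% confidence intervals in that outcome's own unit, for example seconds for time to exhaustion. The planned ANCOVA already provides these.
- A non-central F interval for the index is optional. It needs numerical inversion, so it is more than a hand calculation.

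The cost is a few sentences in 17.1 and a one-line calculation from output already produced, with no new data. The downside is that reported effect sizes become smaller. The corrected index also remains imprecise at 18 (about 25% of null analyses reach 0.06 and about 14% reach 0.14), which is why the verbal labels should go and not merely be attached to the new index.

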1.0 Study Summary

Study Title	Effects of Post-Exercise Recovery Drink Composition on Subsequent Performance in Masters Class Athletes
Study Design	Randomized, Double-blind, placebo-controlled between-subject
Primary Objective	The purpose of this study is to demonstrate that performance in a subsequent bout of high-intensity glycogen depleting exercise will not be significantly different regardless of post-exercise recovery drink (carbohydrate vs. carbohydrate and protein vs. placebo).
Secondary Objective(s)	Assess the level of sports nutrition knowledge and total daily carbohydrate and protein intake in a group of endurance-trained masters class athletes.
Research Intervention(s)/ Investigational Agent(s)	[name], MS, RDN [name] [name] [name] [name], BS
IND/IDE #	
Study Population	Male Athletes, Age 35-59 years
Sample Size	50
Study Duration for individual participants	14 days; 3-4 total visits
Study Specific Abbreviations/ Definitions	Graded Exercise Test (GXT), Maximal Oxygen Consumption (VO ₂ max), Plateau in Oxygen Uptake (VO ₂ peak), High-Intensity Aerobic Interval Exercise (INT), Time to Exhaustion (TTE), Heart Rate Variability (HRV), Sweat Rate (SR), Carbohydrate (CHO), Carbohydrate-Protein (CHO-P), Placebo (PLA), Masters Class Athletes (MCA's)

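### A non-significant test cannot establish the Section 1.0 aim or the third hypothesis (CHO-P no better than CHO): no margin or confidence interval is planned, and the 0.90 power is for the three-group ANCOVA only

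*Combined protocol and SAP*

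**What the plan says.** **Aims.** The primary objective in Section 1.0 is to demonstrate that performance in the second bout "will not be significantly different regardless of post-exercise recovery drink", and it names all three drinks, placebo included. Section 2.1 states the purpose neutrally, as examining the effects of the drinks. Section 2.2 gives three hypotheses: CHO significantly better than placebo (PLA), CHO-P significantly better than PLA, and CHO-P not significantly better than CHO.

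**Analysis.** Section 17.1 plans a one-way ANCOVA for each outcome, including time to exhaustion (TTE), with the pretest value as covariate. Pairwise comparison is conditional: "If the ANCOVA is significant", Fisher's "LSD Post-Hoc analysis will be used to determine group differences". The effect measure is partial eta squared. No margin, equivalence test or confidence interval is mentioned.

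**Sample size.** Section 17.2 states: "The total sample size was determined to be a total of 18 (6 in each group) based on a one-way ANCOVA, power of 0.90", at alpha 0.05. The source is pilot data in young men; the pilot effect, SD and n are not given. It adds that "due to potential dropout rates, a total of 30 participants (10 per group) will be recruited with the goal of completing 18".

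**Counts elsewhere.** Section 1.0 lists the sample size as 50. Section 12.2 says "Participants will be recruited and screened until a maximum of 50 individuals are enrolled", expects that "the number of recruited individuals will likely exceed the number of enrolled participants", and then says "However, no more than 50 participants will be recruited".

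**The concern.** The 1.0 aim and the third hypothesis are worded as absence of significance. The planned test can find a difference but cannot show that there is none. If the ANCOVA is not significant, the plan gives no CHO-P versus CHO comparison at all, although that is the result the 1.0 wording looks for. The smaller the trial, the more likely that result is, whatever the truth.

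The risk is not remote on the protocol's own background: Section 3.0 cites two occasions in younger athletes where CHO-P went with better subsequent performance or a smaller decline. A real CHO-P benefit could be missed here and reported as no difference between drinks.

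The aims also conflict. If 1.0 is right, the first two hypotheses in 2.2 are wrong, so the plan does not say which result would support it.

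**Working it through.** **Inputs.** From 17.1 and 17.2: three equal groups, one covariate, alpha 0.05, power 0.90, N = 18 completing and 30 recruited. From 1.0 and 12.2: 50, taken as about 16 per group. No SD or effect size is given, so differences are in residual (covariate-adjusted) SD units and every effect below is an assumption.

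**1. The plan's own figure.** N = 18 cannot be reproduced forward without the pilot effect. Solving backward, with numerator df 2 and denominator df 18 − 3 − 1 = 14:

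0.90 = P[F(2, 14; noncentrality 18·f²) > 3.74] gives f = 0.938, and partial eta squared = f²/(1 + f²) = 0.468.

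This is the smallest effect at which N = 18 gives 0.90 on the standard reading (overall test, numerator df 2). It is covariate-adjusted, so the raw effect could be smaller: about 0.31 or 0.14 if the pre-post correlation were 0.7 or 0.9 (assumptions).

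**2. Precision for CHO-P minus CHO.** With a balanced covariate, the half-width is t(0.975; 3n − 4)·√(2/n):
- n = 6: 2.145 × 0.577 = 1.24
- n = 10: 2.056 × 0.447 = 0.92
- n = 16: 2.015 × 0.354 = 0.71

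Allowing for chance covariate imbalance (simulated ANCOVA, random covariate), the mean half-widths are 1.26, 0.93 and 0.72.

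**3. Detection under the 17.1 rule.** Simulation of the overall F test followed by LSD, 100,000 runs per cell or more, residual SD 1, CHO = 0, CHO-P = 0.8, PLA mean varied from −2.4 to +0.8:

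| Per group | 95% CI half-width (SD) | 0.8 SD detected, ANCOVA then LSD | 0.8 SD detected, without the ANCOVA step |
|---|---|---|---|
| 6 | 1.26 | 15-24% | 24% |
| 10 | 0.93 | 27-40% | 39-40% |
| 16 | 0.72 | 46-59% | 59% |

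The range reflects where PLA lies; the lowest values occur with PLA midway between the other two.

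**4. At the back-solved effect, f = 0.938.**
- Equally spaced means PLA < CHO < CHO-P (assumed): gap = f·√1.5 = 1.15 SD. CHO-P versus CHO is detected 43% of the time at 6 per group, 68% at 10 and 88% at 16.
- CHO = CHO-P > PLA (assumed): gap = f·3/√2 = 1.99 SD. Each drink-versus-PLA contrast is detected 83% of the time at 6 per group and 98% at 10.

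The random covariate lowers overall power slightly, to 0.88 rather than 0.90 at N = 18 in these simulations.

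**5. Counts.** 1 − 18/30 = 0.40, so 17.2 implies a 40% loss without stating a rate. Thirty lies within a maximum of 50. In 12.2, recruited cannot exceed enrolled if enrolment reaches 50 and recruitment is capped at 50.

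**The case against.** - **No success rule is written down.** The plan does not say that non-significance will be declared a success; this follows from the wording of 1.0 and the third hypothesis, and 2.1 is neutral. That is fair. But 17.1 provides nothing else on which to judge those two claims, so the gap remains.
- **The percentages rest on assumed effects.** True: with no SD given, 0.8 or 1.15 SD cannot be turned into seconds, and nobody can say whether either would matter to an athlete. The logical point needs no assumed effect, and the half-widths need only the group sizes.
- **At about 16 per group the picture is better.** It is: the half-width falls to 0.72 SD and detection of 1.15 SD rises to 88%. The problem is not uniformly severe. Even so, an assumed 0.8 SD difference would be missed 41-54% of the time.
- **The design is not weak everywhere.** Also true. Under CHO = CHO-P > PLA at the back-solved effect, the placebo contrasts have 83% and 98% power, so a null result would be some evidence against very large effects over placebo. Low power works against the first two hypotheses in 2.2, not for them.
- **The counts may be reconcilable.** Section 12.2 defines enrolment after consent, questionnaires and anthropometrics, before the VO₂peak criterion in 10.2 is applied. Fifty could therefore include men later found ineligible. No sentence says so, but this reduces the matter to a clarification.

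**Conclusion.** The inference point stands. As planned, a non-significant result cannot establish the 1.0 aim or the third hypothesis in 2.2, and 1.0 contradicts the first two hypotheses. At the 18 completers that 17.2 aims for, the interval for CHO-P minus CHO would run about 1.26 residual SD either side of the estimate, and an assumed 0.8 SD difference would be found at most about a quarter of the time. This should be fixed before the analysis.

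Three stronger readings are not supported. A reader might infer that N = 18 is wrong; the pilot effect is not given, so it can be neither reproduced nor refuted. A reader might infer that 30 and 50 contradict each other; 12.2 gives 50 as a maximum and 30 does not breach it. A reader might infer that the trial is underpowered for all its hypotheses; the weakness shown here lies mainly in CHO-P versus CHO.

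The detection rates depend on the assumed effects and on the PLA mean. The conclusion about interpretation does not.

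**What to change.** None of this needs more participants or a change to randomisation or the ANCOVA.

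1. **Section 17.1:** report the adjusted CHO-P minus CHO difference in TTE with its 95% CI whether or not the ANCOVA is significant, and base the conclusion on that interval.
2. **Sections 1.0 and 2.2:** reword the primary objective as estimating and comparing the effects of the drinks, in line with 2.1 and without contradicting the first two hypotheses. Reword the third hypothesis so that non-significance is not read as no difference.
3. **Section 17.2:** label the 0.90 as power for the overall three-group ANCOVA only.
4. **Minor clarification:** say how the maximum of 50 in 1.0 and 12.2 relates to the 30 recruited and 18 completing in 17.2, and make the recruited and enrolled sentences in 12.2 compatible.

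The cost is protocol wording and one extra reported interval. The downside is a more limited conclusion: at these group sizes the interval may well be too wide to call the two drinks alike.
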